6.3.2. CHW Supervision

CHWs are not clinicians and they often struggle with many of the same issues as their clients in terms of health problems, children, housing, and poverty. This allows them to intimately understand the challenges their clients face and usually translates into strong bonds between CHWs and clients, but it sometimes transforms into a significant burden when clients struggle with serious issues. The CHWs also must deal with the stresses of home visitation (safety, cleanliness, hectic households, and poverty) and the pressures of executing a new non-clinical role in clinical and WIC settings. In order for CHWs to successfully perform their job, they require adequate supervision and support. Supervision is best conducted using a team approach with a group of CHWs to facilitate

self-discovery and group learning. In CO-OP Chicago, CHWs will report directly to the CHW supervisor (the CO-OP Chicago project manager) for day-to-day supervision and support. [name] and the project manager will ensure the CHW roles are properly explained to clinical staff and faculty in the participating clinics. [name] will provide a similar role within the WIC sites. CHWs will meet with the CHW supervisor weekly. Every two weeks, CHWs will also meet with the CHW supervisor, [name], [name], and [name]/[name] (rotating) for discussion of clinical issues, self-management skills support, and for continuing education. [name] will meet with CHWs on an as-needed basis to discuss mental health issues related to participants or the CHW job and to generate strategies for resolution.

6.3.3. Fidelity Monitoring

CHWs will have a caseload of up to 70 patients, each of whom will receive 4 visits and follow-up calls over one year. CHWs will complete documentation after every encounter to record visit location, duration, oral health curriculum topics covered, resources utilized, issues encountered, and family members who participated. This form is in Appendix I. These data will be reviewed monthly by the CHW supervisor and investigators to ensure consistency and fidelity of the intervention content and also to inform the study team about areas of focus and challenge. Reports from these data will show core curriculum topics covered and pending per patient, resources used, and overall trends in topics. While the goal is to cover each of the core curriculum topics over the duration of the intervention with each family, CHWs may deviate due to family needs and resources. Deviations will be reviewed; if they are due to CHW issues (lack of comfort with a topic or poor organization), additional training will be provided either to the specific CHW alone or to the group as needed. These data will also be used in final analyses to determine "dose" of intervention and assess the influence of specific topics/skills on outcomes.

The CHW supervisor will accompany each CHW on a minimum of one visit out of every 30 (8% of total visits). The CHW supervisor will assess the CHW using the CHW Fidelity Assessment Form (Appendix I). If a CHW scores less than 4 on any category, additional training and support will be provided to the CHW. Depending on the specific issue, additional training/support could include extra sessions with the investigators, and/or more shadowing experience with more experienced CHWs and/or in the dental clinic. Additional visit supervision and fidelity scoring will be implemented until the CHW is consistently scoring 4 on all categories.

6.4 Assessment of Subject Compliance with Study Intervention

Subject compliance is defined and measured in two ways. First, we will measure compliance with the CHW visit protocol, meaning how many of the four in-person visits and two follow-up phone calls are completed in the 12-month intervention period. This is assessed using the CHW documentation (number of visits/calls completed). Families that are not compliant will have less CHW encounters. Second, we will monitor participant compliance with goals. This is determined using the Action Plans (Appendix

E) that are completed at each in-person visit. The Action Plan documents record the goals and the CHW Encounter Tracking Form (Appendix H) records progress, or lack of, regarding these Action Plans (goal achieved, partially achieved, or not achieved at all).

7 STUDY SCHEDULE

7.1 Screening

Screening Visit with RA (prior to Baseline Visit)

- Obtain and document verbal consent from potential caregiver subject on screening consent document.
- Ask the potential caregiver subject screening questions to determine eligibility.
- Perform brief visual examination needed to determine eligibility of the child subject.
- Describe the study procedures and show the recruitment video (if interested).
- Schedule study enrollment visit for individuals who are eligible, interested, and available for the duration of the study.

7.2 Enrollment/Baseline Visit with RA (Visit 1, prior to Randomization)

- Obtain and document consent from subject on study consent form.
- Verify inclusion/exclusion criteria.
- Obtain self-reported data via verbal questionnaire. This includes demographic information, oral health behaviors, oral health risk factors, medical history questions, and family psychosocial functioning.
- Weigh child.
- Apply disclosing solution to child's teeth and obtain photographs for plaque assessment.
- If conducted in home, observe child brushing teeth and brushing equipment.
- Explain to family the randomization process and when intervention will start (Intervention will begin after randomization for families in sites that are randomized to receive CHW services. For families in sites that are randomized to not receive CHW services, they will be offered CHW services after study completion in one year.)
- Verify contact information.
- Thank family. Offer remuneration and give flyer on basic oral health recommendations.

7.3 Randomization, Day 0

Each site will be randomized to CHWs or usual care once recruitment is completed or near completion. See Section 5.4.1. for details.

7.4 Intervention in-person visits for CHW-sites only, start Day 1 and complete by Day 365

Four in-person visits will be offered to families. See Appendix D for details. The first two visits will be delivered between days 1-179. The third and fourth visits will be delivered between days 180-364.

7.5 Intervention telephone follow-ups for CHW-sites only, start Day 2 and complete by Day 365

Four follow-up telephone calls will be offered to families. The plan is for follow-up telephone calls to follow in-person visits.

7.6 6-Month Visit with RA, Day 180 (- 14 days, + 60 days)

- Obtain self-reported data via verbal questionnaire. This includes demographic information, oral health behaviors, oral health risk factors, medical history questions, and family psychosocial functioning.
- Weigh child.
- Apply disclosing solution to child's teeth and obtain photographs for plaque assessment.
- If conducted in home, observe child brushing teeth and brushing equipment.
- Record adverse events as reported by subject or observed by investigator.
- Verify contact information.
- Thank family. Offer remuneration.

7.7 Final Study Visit with RA, Day 365 (+ 90 days)

- Obtain self-reported data via verbal questionnaire. This includes demographic information, oral health behaviors, oral health risk factors, medical history questions, and family psychosocial functioning.
- Weigh child.
- Apply disclosing solution to child's teeth and obtain photographs for plaque assessment.
- If conducted in home, observe child brushing teeth and brushing equipment.

- Record adverse events as reported by subject or observed by investigator.
- Remind family that we will send families a copy of the study results at the end of the study. Results will also be posted on the study website and displayed at the clinic/WIC center. Remind families that if they are in the usual care arm, they will soon receive a phone call from a CHW offering them a visit. Remind them that we may contact them in the future for follow-up studies if they agreed to that at the time of consent. Verify contact information.
- Thank family. Offer remuneration.

7.8 Intervention in-person visits for usual care-sites only, start Day 1 after final day collection and complete end of study

Families that are in usual care sites will be offered one CHW visit after they complete the final data entry. This is a courtesy visit to assess family risks and refer them to existing resources. The window for completion of this visit will last as long as funding is available for the CHWs.

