4 STUDY DESIGN

- CO-OP Chicago is a two-arm cluster randomized controlled trial with repeated measurements. The comparison arm receives usual care. (After completion of the trial, the usual care arm will be offered limited CHW intervention.) The nature of the intervention allows for a single blind design in which data collection will be performed by research assistants.
- The trial targets healthy, low income, predominantly minority children under the age of 3 years old, and their families in Cook County, Illinois.
- This is a multi-center trial with two arms and 20 sites (clusters).
- We will recruit between 18-23 families from each site for a total sample size of 420. Sites are in two strata: medical clinic and WIC. These are combined for the primary analysis but will be compared to each other in the exploratory analysis.
- Study enrollment is scheduled to be completed in approximately 12 months. The primary recruitment will occur in the first 10 months, and the last two months will allow for unexpected delays.
- Participants will undergo study procedures for 12 months (+ 3 months).
- Participants will be recruited from each of the 20 study sites. Once recruitment at
 a site is completed, the site will be randomized and participants will be informed
 of the arm allocation. Participants assigned to the CHW arm will then be offered
 four CHW in-person visits and four follow-up phone calls over 12 months. The
 expectation is that in-person visits will align with well-child checks/WIC
 appointments every 3 months, so two visits in the first six months and two visits
 in the second six months, although the schedule is flexible. Telephone follow-up
 calls will follow in-person visits at a time determined meaningful by the CHW and
 family. Participants assigned to the usual care arm will be offered a CHW visit
 after they complete the final data collection at 12 months.

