5.4.2 Masking Procedures

Although double blinding in a behavioral randomized clinical trial is not feasible, blinding will be maximized by utilizing independent outcomes assessors (research assistants) who will be blinded to study arm, and by reminding staff and partners about equipoise. Participants will be reminded at every contact to not disclose their study arm or any intervention they are or are not receiving. Investigators who supervise the CHWs and the project manager will be unblinded to treatment arm because they will need to work with the CHWs and monitor intervention fidelity and data accuracy. The USCF CC will also be unblinded to treatment arm. Study staff and investigators will not have access to interim outcomes data. Unmasking procedures are described in more detail in the Manual of Procedures.

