APPENDIX D: CONTACT ATTEMPT AND WINDOW PROTOCOL

CO-OP Chicago

CONTACT ATTEMPT AND WINDOW PROTOCOL

Research Specialist: Data Collection

Windows

Type of Visit	Earliest start	Latest acceptable	
Baseline	NA	NA	
6-month	14 days before	60 days after	
12-month	Date due	90 days after	

Clock starts when randomized.

12-month due date does not change regardless of when 6-month data collection visit completed.

Attempts

- For main outcomes visit: 12-month
 - These are primary outcomes, need to try to get at all costs.
 - Contact every 2-4 days at varying times of day and varying types of mediums for first 2 weeks. Consider then reducing frequency of attempts but do not give up until window closed.
 - If phone not working, or no answer after 5 attempts, stop by home up to 2 times. If can talk with family, great. If not, then drop off letter.
 - If cannot drop off letter or no response to dropped off letter after 1 week, send certified letter.
 - o If no response to anything, at minimum try to call once a week until window closed.
 - o If ultimately family cannot do in person, do via telephone if feasible for family.
 - If phone not working/no answer, attempt to verify address and phone number at the subject's clinic/WIC.
 - If no answer from all phone numbers and letters, attempt to see if any scheduled appointments at subject's clinic/WIC. If yes, try to be at that appointment to talk with family before/after.
 - Track for each attempt
 - Date
 - Day of week
 - Time of day
 - Medium (phone call, text, email, letter, stopped at home) and number/address used
 - Comment section (note if family answered but can't talk now, family stood you up, talked with other family member and told to call back, etc)
- For 6-month
 - Same as 12-month but shorter window.

CHWs

Windows

4 visits over 12 months, preferred in person at home or other location face-to-face. Goal is 2 visits in first 6 months, 2 visits in second 6 months. Follow-up phone calls should be conducted after visits (total of 4).

- Additional contacts acceptable but not encouraged.
- CHW can call family to schedule as soon as randomization completed.
- Goal is one visit every 2-3 months
- No more than 2 in-person visits before the six month mark; no more than 2 in-person visits after the six month mark
- In-person visits cannot be closer than 30 days.

Attempts

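### The masked research assistant's final-visit script raises the usual-care CHW call, which can prompt a reply that reveals a whole site's arm while other families there are still to be assessed

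*Combined protocol and SAP*

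**What the plan says.** **Masking.** Section 5.4.2 relies on "utilizing independent outcomes assessors (research assistants) who will be blinded to study arm", because double blinding is not feasible. It adds a rule for families: "Participants will be reminded at every contact to not disclose their study arm or any intervention they are or are not receiving". The project manager is listed among the unblinded staff.

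**Final visit.** Section 7.7 is an RA visit at Day 365 with a 90-day allowance. After outcome collection and adverse events, its task list includes: "Remind families that if they are in the usual care arm, they will soon receive a phone call from a CHW offering them a visit".

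**Allocation and clock.** Section 5.4 sets each family's arm by its site. Section 5.4.1 randomizes a site at about 90% of its enrollment goal. Appendix D states: "Clock starts when randomized". It fixes the 12-month due date whatever the date of the 6-month visit.

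**Usual-care CHW visit.** Section 7.8 says: "Families that are in usual care sites will be offered one CHW visit after they complete the final data entry". Its heading gives the timing as "start Day 1 after final day collection and complete end of study". The last bullet of Section 4 that describes the arms uses the same family-level trigger. The first bullet of Section 4 reads differently: "After completion of the trial, the usual care arm will be offered limited CHW intervention".

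**The concern.** Sections 5.4.2 and 7.7 pull in opposite directions. One asks families to say nothing about the intervention. The other has the masked assessor raise it with every family. Natural answers, such as saying that a CHW has already been coming or asking when she will call, give the arm away.

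In an individually randomized trial such a remark, made after the family's own outcomes were recorded, would do little harm. Here the arm belongs to the site, so the remark carries forward to every family there that is not yet assessed. At those later visits the RA asks the co-primary brushing question aloud (Section 8.1). In home visits the RA also records brushing duration and caregiver assistance directly, which are secondary outcomes. An assessor who knows the arm may ask, prompt or record differently. The direction of any resulting bias cannot be predicted.

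**Working it through.** The plan gives no figure on masking to reproduce. The check is a reading of the timing, followed by an illustration.

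**Overlap in time.** Families enrolled before site randomization share one arm and one due date. The window runs from Day 365 to Day 365 + 90 = Day 455. A family seen on Day 365 has heard the sentence that day, and under Section 7.8 a usual-care family can be offered its CHW visit from Day 366. Other families at the site can still be assessed until Day 455, an overlap of up to 90 days. The documents do not say how the clock runs for the roughly 10% of families who may enroll after site randomization.

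**Families seen per site.** The target is 420 families over 20 sites, a mean of 21. Section 12.2 assumes 15% attrition at each follow-up.
- 15% applied once: 21 × 0.85 = 17.9
- 15% applied twice: 21 × 0.85² = 15.2

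So m, the number seen at 12 months, is about 15 to 18. When the first family finishes, m − 1 = 14 to 17 are still due. When an average family finishes, (m − 1)/2 = 7 to 8.5 are.

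**Share of visits made after a disclosure.** Let q be the chance that a completed family reveals its arm, independently of the others, and let one RA team serve the site. Neither q nor the one-team arrangement is in the documents. The k-th visit follows at least one disclosure with probability 1 − (1 − q)^(k−1). The mean over k = 1 to m is

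1 − [1 − (1 − q)^m] / (m q).

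For q = 0.05 and m = 15: 0.95^15 = 0.463, so 1 − 0.537/0.75 = 0.284.

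| q (assumed) | m = 15 | m = 18 |
|---|---|---|
| 0.02 | 13% (1.9 visits) | 15% (2.8 visits) |
| 0.05 | 28% (4.3 visits) | 33% (5.9 visits) |
| 0.10 | 47% (7.1 visits) | 53% (9.5 visits) |

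This is the relevant measure because a disclosure at the last visit affects no later assessment. The chance of any disclosure at all by the end of the window would be larger, but it is not a measure of harm.

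**Which outcomes are exposed.** Brushing frequency is asked by the RA. Brushing is also observed by the RA when the visit is at home. For plaque, the RA applies the disclosing solution and takes the photographs, and Appendix C bases retakes on whether the incisors are captured with enough clarity and light, not on the amount of plaque. A calibrated clinician then scores the images (Section 4).

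**The case against.** The strongest defense is that the sentence is neutral. It is conditional, can be read identically to every family, comes after that family's outcomes, and largely repeats what the RA said at baseline under Section 7.2. Families already know their arm from the mailed letter. The non-disclosure reminder applies at this visit too, and Section 5.4.2 refers to further unmasking procedures in a Manual of Procedures that is not part of these documents. All of this stands, and it rules out reading the script as an unmasking in itself. It does not answer the point about later families at the same site, because the sentence still invites the reply that the reminder tries to prevent.

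A second defense is that arm may leak anyway, at the 6-month visit, during the interview or while scheduling. That also stands. The table describes disclosure at an assumed rate and does not isolate what this sentence adds.

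Three stronger readings are tempting, and the documents do not support them:
- **Plaque is biased in the same way.** Scoring by another person from photographs, with retakes judged on image quality, makes this a weak route. The documents do not say whether the scorer is masked.
- **Waiting control families are contaminated.** Section 7.8 does let CHW contact begin while other control families at the site are unassessed, so this is possible. But it describes a single courtesy visit and gives no location, and nothing shows that content would reach other families. It cannot be quantified.
- **Section 7.2 contradicts Section 7.8.** Section 7.2 tells families that the offer follows study completion in one year. Appendix A labels the family's own Day 365 visit as study completion, so the two can be read consistently. Only the trial-level wording in the first bullet of Section 4 remains out of line.

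**Conclusion.** The point holds as an avoidable weakness in assessor masking, not as a fatal flaw. The masked RA is scripted to raise the one topic that families are asked not to discuss, and cluster allocation makes any revealing reply informative about every unassessed family at the site. The risk falls mainly on self-reported brushing, one of the two primary outcomes, and on RA-observed brushing behaviors.

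Under assumed disclosure rates of 2% to 10%, with one RA team per site and 15 to 18 families seen, between about 13% and 53% of a site's 12-month visits would follow an earlier disclosure. The part due to this sentence is unknown, and so are the size and direction of any bias in the estimated effect. The case for change rests on how easily the prompt can be removed, not on a demonstrated bias. The timing wording in Section 4 is a separate and minor matter.

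**What to change.** Delete the usual-care sentence from the RA's task list in Section 7.7. Have the project manager, who is already unblinded, give the notice after the family's final data collection, or send it by the mailing that UIC already uses under Section 5.4.1 to tell families their assignment. Keep the non-disclosure reminder at the visit.

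Separately, reconcile the first bullet of Section 4 with its later bullet on the arms and with Section 7.8, so that the documents state one trigger for the usual-care CHW offer. Whoever settles the wording should note that, as Section 7.8 stands, CHW contact can begin while other control families at the site are still unassessed. No particular visit timing is proposed here.

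The cost is one script line removed, one extra letter or call per family, and a wording amendment. Families would hear of the courtesy visit slightly later. Sample size and analysis are unchanged.

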7.9 Withdrawal Visit

If a subject withdraws from the trial or is administratively withdrawn, no more data collection will occur.

8 STUDY PROCEDURES /EVALUATIONS

8.1 Study Procedures/Evaluations

Location

Because data collection would ideally occur in the homes by RAs, the home will be presented to families as the preferred location. Families that agree to home data collection will be given first priority in enrollment. Some families may be uncomfortable with home data collection for a variety of reasons including trust, not being on the lease at the place they live, or feeling that the home is unclean or unsafe. Families that want to participate but cannot agree to a home visit will be scheduled for data collection in their site of recruitment (WIC or clinic) or another location where the plaque measurement can be performed. Once families have interacted with project staff and better understand the study, they may agree to future data collection and intervention visits in the home. For the 6- and 12-month data collection of the study primary outcomes is the most important factor regarding data collection location.

Survey development

Most survey questions were drawn from NHANES, NHIS, and the previous EC4 consortium, or are published survey instruments. A few questions were developed by the CO-OP Steering Committee to capture variables of interest for this research. The questions and question sources are shown in Appendix B. Primary domains are brushing behaviors, oral health risk factors, and demographics. These questions were informed by the clinical expertise of the investigators as well as the investigators' experience doing home environmental assessments for research purposes.⁴⁶⁻⁴⁷

Data Collection

All instruments will be in the preferred language of the caregiver. The RA will verbally ask study questions to the participants, using visual prompts to show response options. The RA will record answers on a portable laptop computer unless Wi-Fi is not available or the computer malfunctions, in which case paper forms will be used. An exception to this are the questions from the PROMIS scales. The RA will administer the PROMIS questions in the same way as the other questions with one exception; if the environment does not seem to offer sufficient privacy or the caregiver seems reluctant to verbally answer these questions, the RA will offer the caregiver the option of completing the questions on the computer (handing the computer to the participant to complete) or on a paper version with pen/pencil. The decision between computer or paper will be made based on the respondent's comfort with computers. Our experiences in similar populations and in the pilot phase of this project have suggested that the reading ability of many adults is limited, and they usually are more comfortable when they are read the questions, even when the questions are sensitive. The PROMIS depression, anxiety,

and functioning scale is not a clinical tool and does not have a clinical cut point that requires action.³⁵⁻³⁶ RAs will offer a list of mental health resources to all participants at the conclusion of the PROMIS questions.

Next, the following procedures will be performed:

Plaque measurement: A RA will apply disclosing solution to the anterior maxillary incisors while another RA photographs the teeth. The images will be verified for accuracy. A dental hygienist or dentist will obtain a plaque score from the photographs, following the Simplified Oral Hygiene Index - Maxillary Incisor (OHI-MIS) described by Greene and Vermillion.⁴⁸ The detailed protocol is in Appendix C.

Tooth brushing observation: The RA will observe the child's tooth brushing, including any caregiver assistance with this activity and the equipment used for brushing. The RA will document the steps of brushing, caregiver involvement in the process, the time of active brushing, and equipment used.

Data fidelity

The UCSF Coordinating Center (CC) is developing a gold standard calibration protocol for examiners of plaque. This will include the specific requirements of images and will ensure scoring of images is consistent. (Also see Section 14). RAs will practice application of the disclosing solution and image obtainment under the supervision of study investigators until they demonstrate they can consistently collect quality images for scoring. They will then review the plaque measurement procedures monthly with investigators.

RAs will practice collection of all questionnaire and behavior observation data, and then two RAs will simultaneously collect data (double data entry) from practice participants (and sometimes real participants) until 95% concordance between RA-collected data is observed. The RA field supervisor will then observe and double code one out of every 30 data collections to ensure fidelity. If errors are noted or concordance is less than 95%, the RA will be required to practice additional data collection under the supervision of the field supervisor until 95% concordance is achieved.

